8.6 SAFETY OVERSIGHT

Monitoring for adverse events will be conducted in real-time by the study investigators and study coordinators. Risks involved with this study are considered greater than minimal risk. For this reason, we will utilize the standing independent Data Safety Monitoring Board (DSMB) as chartered by the Center for Clinical and Translational Science (CCTS). The DSMB will meet semiannually or as needed, and will review subject recruitment, AE's, side effects, laboratory results, dropouts, protocol violations, and inclusion/exclusion criteria. More frequent meetings will take place if side effects or other problems are prevalent.

9 CLINICAL MONITORING

Clinical site monitoring will be performed by Bluegrass Research Consultants Inc. The monitor will conduct monitoring to verify that a) the rights and well-being of human subjects are protected; b) the reported trial data are accurate, complete and verifiable from source documents; c) the conduct of the trial is in compliance with the currently approved protocol/amendment(s), Food and Drug Administration (FDA) regulations and ICH guidelines d) Provide practical guidelines for Site Monitors, Study Monitors and Medical Monitors; e) Provide consistent monitoring procedures across all clinical sites; f) Ensure the quality and integrity of clinical study in a timely manner. A monitoring visit report will be provided to the Sponsor within 21 business days following the completion of a visit.

The first monitoring visit will be conducted within two weeks following enrollment of the first subjects. Subsequent monitoring visits will be completed based on enrollment and are expected to occur every four to six weeks.

10 STATISTICAL CONSIDERATIONS

10.1 STATISTICAL AND ANALYTICAL PLANS

10.1.1 GENERAL APPROACH

Sample Size and Power Analysis - The primary outcome aim of the study is to determine if treatment with the study medication results in greater improvements in patient-reported outcomes one year following surgery. We will use the validated Knee Osteoarthritis and injury Outcome Score (KOOS),[27] which is a self-administered, knee-specific instrument that evaluates the course of knee injury and treatment outcomes. To reduce the risk of an underpowered RCT, an a priori sample size estimation was calculated from data collected from recent studies of ACL-injured and -reconstructed patients.[28-32] The previously published oneyear KOOS Quality of Life Scores are 60.2 ± 24.2 [31] and the minimal detectable change of this instrument is 7.2 [32]. Assuming that the standard deviation of the change scores between the day of surgery and one year postoperative visits will be 20% of the standard deviation of the standard deviation of the one-year KOOS Quality of Life Scores ($.2 \times 24.2 = 4.8$), a sample size of 16 patients per group (32total) would be at least 80% powered to detect a difference of 7.2 points between the treatment group and the control group (One-way ANOVA model with alpha = 0.05, Effect size = 7.2/4.8 = 1.5, G*Power 3.0.10). This sample size would adequately power the study for the primary outcome variable, but would also adequately power the study for the second aim of the study. The second aim of the study is to compare chondrodegenerative biomarkers between groups at the 1 year follow up. We have previously observed large effect sizes between groups in preliminary studies (ES = 1.34), and a sample size of 32 patients (16 per group) would be at least 80% powered to detect effect sizes of this magnitude. However, to protect against an underpowered study due to patient attrition, we will monitor compliance and potentially enroll up to 20 patients per group in order to adjust for attrition. Patient costs will not occur until sample or MRI analysis.

The power calculations include several caveats. First, for purposes of power calculation, we did not assume a full repeated measures analysis, but instead analyzed at a single time point (oneyear follow-up). Second, we note that in trials such as this, the power of a non-parametric analysis is never much lower than its parametric analog (the "asymptotic relative efficiency" of the Wilcoxon test is at least 0.95), leading us to conclude that our parametrically based power calculations should apply with equal force to a non-parametric analysis.

Statistical analyses - Results from a sample of this size may not be normally distributed. Therefore, non-parametric statistical measures may be used. Primary outcome measures evaluating for change in KOOS will be assessed at multiple points and will be analyzed for change between groups using Friedman two-way ANOVA for repeated measures. Synovial fluid analyses comparing the three groups at five time points will be analyzed using the Wilcoxon Signed Rank Sum Test with Hochberg corrections for multiple time points. Alternatively, if results are normally distributed or can be transformed (e.g., by log transformation) to meet the criteria for normality for parametric analysis, then repeated measures ANOVA will be utilized comparing treatment groups. P-values of less than or equal to 0.05 will be considered statistically significant.

Predicted Results: IL-1ra, while potent, has had mixed results in the treatment of established OA, possibly due to it's short half-life in vivo. In this trial, we expect that an early intervention with IL-1ra will effectively block the deleterious cascade of joint degradation events after joint injury. We expect a significant effect of IL-1ra on post-injury pain and concomitantly an increase in patient-reported outcomes due to the improved early function

Minimization of bias: Due to the randomized study design and the blinding of the investigator and patient to the drug used, we hope to eliminate any investigator or subject bias. Using broad and previously established enrollment criteria we hope to reduce selection bias to a minimum while protecting potentially vulnerable individuals through the exclusion criteria. Procedural bias and measurement bias will be reduced by the multicenter design and the blinded data analysis.

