- To assume responsibility for the proper conduct of the study and not to deviate from the procedures described in the protocol.
- I am thoroughly familiar with the investigational product(s) as described in the protocol, Investigator's Brochure and any other relevant information sources provided to me.
- I am aware of and will conduct the study in compliance with the protocol, ICH GCP guidelines and all applicable regulatory requirements.
- I agree to permit monitoring and auditing of the study by the Sponsor and its designates, and inspection by appropriate regulatory authority (ies).
- I agree to ensure that all persons assisting with the conduct of the study are properly qualified for their function.

Investigator Name & Signature:

Principal Investigator: [name] Print/Type Name

Signed: _____

Signature

[figure not shown]
Date:

PROTOCOL SUMMARY

Title:	A Prospective, Multicenter, Randomized, Triple-Blinded, Placebo-
	Controlled study of IL-1RA Treatment in Patients with Acute ACL
	Tear and Painful Effusions
Précis: Objectives:	This study aims to establish efficacy and timing of administration, to reduce post-injury pain, decrease inflammatory biomarkers in ACL injured patients undergoing ACL reconstruction and correlate function, patient reported outcomes and MRI findings at 1 years after ACL injury. The study population will include 40 subjects, ages 14-40 who will be randomized into 2 groups (20 subjects per group). 1. Test the efficacy of a treatment protocol using IL-1ra and knee arthrocentesis to alleviate inflammation related knee pain and improve patient-reported outcomes (PRO) following ACL rupture. 2. Determine if intra-articular IL-1ra therapy improves levels of a panel of inflammatory, meniscus and cartilage metabolism, and oxidative stress biomarkers as measured in synovial fluid, serum and urine from patients immediately after ACL injury (baseline, 2 weeks
	after injury and at 1 and 2 years after surgery).3. Answer the question if MRI T1rho changes correlate with synovial biomarker levels and show predictive value for the overall subject patient outcome at 2 years.
Endpoint	Primary endpoint : Change in Patient reported outcomes as measured by KOOS- Symptoms
	Secondary endpoints: KOOS QOL, KOOS-pain, KOOS-Sports/Rec, Biomarker levels in synovial fluid, serum and urine at time of surgery MRI T1rho changes at 2 years
	Study Stopping Criteria

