Using the non-parametric Wilcoxon signed-rank sum test, significant differences (p<0.05) were observed in the anakinra treated group only: Pain was reduced in the anakinra treated group of patients by 23% after 4 days, improvement in Activities of Daily Living by 46%, and improvement in total KOOS by 24%; in contrast the placebo group improved by only 4%, 6% and 7% for these outcomes, respectively. This suggests a significant early effect in this patient population that is beneficial for the early rehab process prior to surgery(22).

Synovial fluid IL-1 α decreased over 1 month in response to a single IL-1Ra intra-articular injection in our pilot trial. The change with treatment (Day 0 to Day 28) in synovial fluid IL-1 α constituted the most intriguing and promising cytokine result from this pilot trial. IL-1 α increased in all the placebo treated patients (n=4 pairs of samples available); whereas IL-1 α decreased in 4 or 5 of the anakinra treated patients (n=5 pairs of samples available)(21).

Study 3: In order to prove that we have the ability to perform a high level (GCP) randomized clinical trial our group has performed a randomized clinical trial involving ACL patients in the same study design featuring identical enrollment (inclusion/exclusion) criteria as the one proposed in this contract (MOON-AAA Clinicaltrials.gov identifier: NCT01692756). In this multicenter early intervention trial testing the effect of Triamcinolone administration patients underwent knee joint aspirations, blood draws and urine collections at three time points prior to ACL surgery.

Table 1: Enrollment data MOON-AAA trial						
	range mean					
AGE	13-33	18.58				
M:F	Male: 25	Female: 18				
BMI	19.1-31.6	24.25				
t visit 1	1-8	4.17				
t visit 2	7-20	11.53				
t surgery	10-51	28.94				

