2.3.2 KNOWN POTENTIAL BENEFITS

IL-1Ra, while potent, has had mixed results in the treatment of established OA, possibly due to its short half-life in vivo. In this trial, we expect that an early intervention with IL-1Ra will effectively block the deleterious cascade of joint degradation events after joint injury. We expect a significant effect of IL-1Ra on post-injury pain and concomitantly an increased improvement in early function.

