4.2 STUDY ENDPOINTS

4.2.1 PRIMARY ENDPOINT

Patient reported outcomes as measured by KOOS-Symptoms

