10.1.2 ANALYSIS OF THE PRIMARY EFFICACY ENDPOINT(S)

A safety review of treatment Groups 1 and 2will be performed. Safety endpoints will be monitored at each study visit and at each monitoring visit.

Study Stopping Criteria

- local intolerance of the administered Kineret or any sign of allergic response.
- development of signs and symptoms before the second time point preventing the second administration of the study drug.
- Any patient reported SAE after the first or second administration of the study drug.
- Diagnosis with any condition as outlined in the exclusion criteria during the course of the initial 2 weeks of study enrollment.

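### The primary KOOS-Symptoms change has no named baseline, one year is not carried into the endpoint, and the only KOOS change the plan writes out starts after the injection

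*Combined protocol and SAP*

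**What the plan says.** The Protocol Summary gives the primary endpoint as "Change in Patient reported outcomes as measured by KOOS- Symptoms". Section 4.2.1 gives "Patient reported outcomes as measured by KOOS-Symptoms", without mentioning change. Neither names a starting visit or an end visit.

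Section 10.1.1 places the primary aim one year after surgery, without a subscale or a starting point. Its analysis paragraph says "Primary outcome measures evaluating for change in KOOS will be assessed at multiple points and will be analyzed for change between groups", using Friedman's method or, if the data allow, repeated-measures ANOVA. It lists no visits and no reference visit. Of the sample size it says "for purposes of power calculation, we did not assume a full repeated measures analysis, but instead analyzed at a single time point", namely one year. Section 10.1.2 is headed as the primary efficacy analysis but holds only a safety review and stopping criteria; its one statement on timing is "Safety endpoints will be monitored at each study visit and at each monitoring visit". Two further horizons appear: the précis refers to one year from the injury, and section 2.2 to two years.

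Under sections 7.3.1 and 7.3.2, KOOS is collected at Visits 1, 2, 4, 5 and 6. Randomisation and injection take place at Visit 1. Visit 2 is the day of surgery or 4 to 6 weeks after injury, and Visit 5 is 12 months after Visit 2.

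One KOOS change is given both a start and an end. It is in the sample-size paragraph of section 10.1.1: "the change scores between the day of surgery and one year postoperative visits". Its standard deviation is set at 20% of the one-year Quality of Life standard deviation.

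**The concern.** A score taken after randomisation and dosing can already contain part of the treatment effect, and this protocol expects it to. Of the earlier randomised pilot, section 2.1 says "This suggests a significant early effect in this patient population that is beneficial for the early rehab process prior to surgery". Section 2.3.2 says "We expect a significant effect of IL-1Ra on post-injury pain and concomitantly an increased improvement in early function". The predicted results in section 10.1.1 attribute the later gain in patient-reported outcomes to better early function. A change measured from Visit 2 would subtract the very benefit that is meant to produce the one-year result.

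At stake is the meaning of the primary estimate. Depending on an unstated choice, it is either the whole effect of treatment at one year, or only the part that arises after surgery.

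**Working it through.** **Step 1. What each place fixes.**

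| Place | Subscale | Start | End |
|---|---|---|---|
| Protocol Summary, endpoint | Symptoms | none | none |
| Section 4.2.1 | Symptoms | none | none |
| Protocol Summary, précis | none | none | one year after injury |
| Section 2.2 | none | none | two years |
| Section 10.1.1, aim | none | none | one year after surgery |
| Section 10.1.1, SD assumption | Quality of Life | day of surgery (Visit 2) | one year after surgery |
| Section 10.1.1, power caveat | none | none | one year |
| Section 10.1.1, analysis | none | none | multiple points |

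If one year after surgery (Visit 5) is taken as the end, two change scores remain: Visit 1 to Visit 5, and Visit 2 to Visit 5.

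**Step 2. The plan's own figure.** The standard deviation is 0.2 × 24.2 = 4.84, stated as 4.8, and the effect size is 7.2 / 4.8 = 1.5. Both reproduce. The 4.8 therefore belongs to the surgery-to-one-year change in Quality of Life. No standard deviation is given for KOOS-Symptoms or for a change from Visit 1.

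**Step 3. What each contrast estimates.** Let dY be the true group difference at Visit 5 and dV2 the group difference at Visit 2. At Visit 1, before the injection, randomisation makes the expected difference 0. Let r be the correlation between Visit 2 and Visit 5, with equal standard deviations assumed.

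- Change from Visit 1: dY − 0 = dY
- Visit 5 with the Visit 1 score as covariate: dY
- Change from Visit 2: dY − dV2
- Visit 5 with the Visit 2 score as covariate: dY − r × dV2

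So each point of dV2 removes 1 point from the change-from-surgery estimate. With Visit 2 as covariate it removes 0.3 to 0.7 point, for an assumed r of 0.3 to 0.7. With Visit 1 as the reference it removes nothing.

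As an illustration only, take dY = 7.2 (the plan's target difference), an assumed dV2 = 3.6 and r = 0.5. The estimates are 7.2 with either Visit 1 method, 7.2 − 3.6 = 3.6 as a change from Visit 2, and 7.2 − 0.5 × 3.6 = 5.4 with Visit 2 as covariate.

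**Step 4. Covariate or change score, both from Visit 1.** They estimate the same quantity. Now let r be the Visit 1 to Visit 5 correlation, again with equal standard deviations. The residual variance is σ²(1 − r²) with the covariate and 2σ²(1 − r) for the change score. The ratio is (1 + r)/2, or 0.65, 0.75 and 0.85 at assumed r of 0.3, 0.5 and 0.7. It is below 1 for any r below 1, so the covariate analysis is the more precise.

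**The case against.** The strongest reply is that the plan does point to an answer. Section 10.1.1 gives one year both as the aim and for power, so a reader who infers that the end is wholly open, and that any pair of KOOS visits would do, goes too far. That part of the reply stands. What remains is that one year is missing from section 4.2.1 and sits beside other horizons.

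The reply can go on that Visit 1 is the natural baseline. The objectives use the word baseline for early biomarkers, section 8.3 uses it for conditions present at screening, and a repeated-measures analysis could include Visit 1. This is fair, but none of that text concerns the reference point for KOOS, and no section closes the gap.

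A reader might also infer that the sponsor intends Visit 2 as the baseline. The documents do not support this. The surgery-to-one-year change is a variance assumption for another subscale, and section 10.1.1 separates the power calculation from the planned analysis. The harm is conditional on that contrast being used.

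Finally, note g to section 7.3.2 lets randomisation precede the MRI, so a reader might doubt that the Visit 1 KOOS comes before the injection. Section 7.3.1 lists KOOS among the assessments reviewed before randomisation, places the injection after randomisation, and note g exempts only the MRI. Stating that the score is pre-injection is at most a clarification.

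**Conclusion.** The concern holds as a gap in the definition of the primary estimand. No baseline is named for the KOOS-Symptoms change. The one-year end appears in section 10.1.1 but not in the endpoint. The only change written out starts after treatment, and using it would remove any Visit 2 group difference one for one.

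The size is unknown. The quantified early results come from an 11-patient pilot and concern pain, daily activities and total KOOS, not KOOS-Symptoms at surgery. A reader might infer a loss of power of a known amount; the documents do not support one. The one-for-one result is algebra that assumes only balance at Visit 1 by randomisation. The 0.3 to 0.7 range also assumes equal standard deviations and the stated correlations. The point should be fixed before unblinding, with moderate confidence in its practical weight, because the plan never says that the Visit 2 contrast will be used.

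**What to change.** In sections 4.2.1 and 10.1.1, define the baseline as the pre-injection KOOS-Symptoms score at Visit 1, and name Visit 5 (one year) as the primary time point. Compare the groups at that visit with the Visit 1 score as covariate, by ANCOVA or by a rank-based version chosen under a rule fixed before unblinding. Do not use the Visit 2 score as baseline or covariate in the primary comparison. Report Visit 2, where the early effect would show, and the remaining visits as secondary. Bring the other stated horizons into line.

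This needs no new visit or questionnaire, since KOOS is already collected at Visits 1 and 5, and it matches the single time point used for power. The cost is that the 4.8 no longer applies: it describes the surgery-to-one-year Quality of Life change. The power statement must be restated for KOOS-Symptoms at one year adjusted for Visit 1, with a justified standard deviation and correlation, neither of which the documents supply.

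### Adequate power is claimed for the primary outcome (KOOS-Symptoms), but it was calculated for a secondary one (KOOS-QOL) with an unsupported change-score SD of 4.8

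*Combined protocol and SAP*

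**What the plan says.** The Protocol Summary gives the primary endpoint as "Change in Patient reported outcomes as measured by KOOS- Symptoms". Section 4.2.1 names the same subscale. Neither gives a time point. Both places list KOOS QOL among the secondary endpoints.

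The sample size paragraph in Section 10.1.1 works from a different subscale: "The previously published oneyear KOOS Quality of Life Scores are 60.2 ± 24.2". It takes 7.2 points as the minimal detectable change of the instrument and then assumes that "the standard deviation of the change scores between the day of surgery and one year postoperative visits will be 20% of" the one-year SD, which gives 4.8 and an effect size of 1.5. From this it states that "a sample size of 16 patients per group (32total) would be at least 80% powered to detect a difference of 7.2 points", and it closes with "This sample size would adequately power the study for the primary outcome variable".

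The same section justifies the number separately for the biomarker aim (effect size 1.34): "a sample size of 32 patients (16 per group) would be at least 80% powered to detect effect sizes of this magnitude". It also allows the trial to "potentially enroll up to 20 patients per group in order to adjust for attrition". A caveat adds that for power "we did not assume a full repeated measures analysis, but instead analyzed at a single time point (oneyear follow-up").

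**The concern.** There are two separate problems.

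1. **The subscale.** The statement about the primary outcome rests on the SD of a secondary outcome. No SD for KOOS-Symptoms appears anywhere, and the 7.2 is not identified as a Symptoms value. Section 7.1.1 itself says that the subscales differ in sensitivity and in how much they change after surgery. The Quality of Life figures therefore cannot be carried over to Symptoms without evidence.

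2. **The change-score SD.** The 24.2 and the 7.2 each carry a reference. The 20% ratio that turns 24.2 into 4.8 does not; only a block citation covers the estimation as a whole. That ratio sets the effect size, and so the power.

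This is the only justification given for the patient-reported primary outcome. The biomarker calculation and the attrition allowance serve other purposes. If the trial shows no difference on KOOS-Symptoms, the result will be read against a statement of adequate power that was never computed for that endpoint.

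**Working it through.** **Inputs from Section 10.1.1:** one-year KOOS-QOL SD 24.2; difference 7.2; change SD 0.2 × 24.2 = 4.84 (rounded to 4.8); alpha 0.05; one-way ANOVA with two groups, which is the two-sided two-sample t-test; 16 per group, rising to at most 20.

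**Formula.** With n per group and d = 7.2 / SD(change), power comes from the noncentral t distribution with 2n − 2 degrees of freedom and noncentrality d × √(n/2).

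**1. The plan's own figure.** d = 7.2/4.8 = 1.5. At n = 16, power is 98.4%. The plan's lower bound of 80% is true on its inputs; 9 per group would already reach it. The biomarker aim, d = 1.34, has 95.6% power at n = 16. The arithmetic is sound, so the inputs are what need checking.

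**2. What a change SD of 4.84 implies.** Let s₁ be the day-of-surgery SD, s₂ = 24.2 the one-year SD, c the change SD and r the correlation between the visits:

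c² = s₁² + s₂² − 2·r·s₁·s₂.

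For fixed c and s₂, the smallest r over all s₁ is √(1 − (c/s₂)²). With c = 4.84 this is √(1 − 0.04) = 0.980, reached at s₁ = √(24.2² − 4.84²) = 23.7. With equal SDs, r = 1 − c²/(2·s₂²) = 0.980 as well. So if the one-year SD is 24.2, no day-of-surgery SD makes 4.84 compatible with a correlation below 0.98.

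**3. What 80% power for 7.2 points needs.**

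| n per group | Detectable d | Largest change SD (7.2/d) | As % of 24.2 | r needed, equal SDs | Smallest possible r |
|---|---|---|---|---|---|
| 16 | 1.024 | 7.03 | 29.1% | 0.958 | 0.957 |
| 18 | 0.961 | 7.49 | 30.9% | 0.952 | 0.951 |
| 20 | 0.909 | 7.92 | 32.7% | 0.946 | 0.945 |

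**4. Sensitivity for KOOS-QOL.** The correlations and the equal SDs are assumptions and do not come from the documents. Change SD = 24.2 × √(2(1 − r)). The 18 column illustrates an assumed 10% loss from 20; the 20 column assumes no loss.

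| Assumed r | Change SD | Power, n = 16 | n = 18 | n = 20 |
|---|---|---|---|---|
| 0.50 | 24.20 | 12.9% | 14.0% | 15.1% |
| 0.75 | 17.11 | 21.1% | 23.2% | 25.4% |
| 0.90 | 10.82 | 44.5% | 49.2% | 53.6% |
| 0.95 | 7.65 | 73.1% | 78.3% | 82.6% |
| 0.96 | 6.84 | 82.1% | 86.6% | 90.0% |
| 0.98 | 4.84 | 98.3% | 99.1% | 99.6% |

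**5. Side case.** If one-year QOL scores alone were compared, the SD would be 24.2 with no correlation involved. Power would be 12.9% at 16 and 15.1% at 20 per group.

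**6. KOOS-Symptoms.** The documents give no SD, no change SD and no target difference identified as its own. Power cannot be calculated.

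**7. Sources.** In the Section 17 list, the entry between 30 and 32 is a serum COMP study in knee osteoarthritis, and entry 32 is a ten-year ACL reconstruction study on loss of knee motion. By title, neither is an evident source for a KOOS-QOL SD or for the 7.2, so these two references need checking.

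**The case against.** The best defence concedes the subscale mismatch and contests the rest.

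- **The ratio is declared as an assumption, under a block citation.** This is correct. Without those sources, one cannot say that the 20% has no basis, only that no specific source is attached to it. That is as far as this point goes.
- **The 0.98 bound depends on the one-year SD being 24.2 in this trial.** This is correct. Section 5 restricts entry to isolated tears at ages 14 to 40 without previous surgery on that knee, so the SD could be smaller. With an assumed one-year SD of 15, the minimum correlation is √(1 − (4.84/15)²) = 0.95 for a change SD of 4.84, and 0.88 for 7.03. These are still high.
- **The lower power figures rest on assumed correlations and on the wrong subscale.** This is also correct. They show how sensitive the plan's calculation is; they do not estimate power for the primary endpoint. The limits of 7.0 and 7.9 need no correlation.
- **The raw-score case is not the planned analysis.** This is a fair point. Section 10.1.1 speaks of change, and its single-time-point caveat most naturally means change to one year. Nothing in the conclusion depends on that case.
- **Early leavers are replaced (Sections 5.4.2, 6.1.9 and 10.2.1).** This limits losses before three months but not later ones, and it affects neither the subscale nor the SD.
- **If power is unknown, so is whether the sample size is sufficient.** This is true. Stating a detectable difference avoids claiming either.

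None of these connects the calculation to KOOS-Symptoms.

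**Conclusion.** The concern holds. The power statement is attached to an endpoint for which no power was computed; this follows from the text alone and needs no assumption. For KOOS-QOL, the statement is true only if the change SD is no more than 29% of 24.2 with 16 evaluable per group, or 33% with 20. The plan assumes 20% and attaches no specific source. Those limits assume a two-sided t-test at 0.05 and a 7.2-point difference.

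The supported conclusion is that adequacy for the primary endpoint is undemonstrated. The documents do not show that the trial is underpowered for KOOS-Symptoms. The statement is wrong as written and must be corrected, because it will frame how the primary result is read.

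**What to change.** 1. Make the primary endpoint (Protocol Summary, Section 4.2.1) and the sizing text (Section 10.1.1) name the same KOOS subscale and the same time point.
2. Delete the 20% assumption and the claim of adequate power for the primary outcome.
3. State what the planned size can detect, for example: *16 (20) evaluable participants per group give 80% power, two-sided alpha 0.05, for a between-group difference of 1.02 (0.91) SD in the one-year outcome of [named primary KOOS subscale]; SD and source: [insert].* If the outcome is a change score, the SD must be that of the change.
4. If power for 7.2 points is still quoted, name the subscale it belongs to, give a range over correlations labelled as assumptions, and check the references for 24.2 and 7.2.
5. Name the baseline visit for change. Under Section 7.3.1, the day of surgery (Visit 2) comes after the study injection at Visit 1, and KOOS is also collected at Visit 1. The wording should also cover participants who do not have surgery.

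**Cost:** wording changes, one sourced SD for the named subscale and a stated baseline visit. The 16 to 20 per group can stay, with no added patients. The drawback is that the stated power becomes less favourable.
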